### Death

The following death summaries will be generated:

- Number (%) of patients who died by study period (TEAE and post treatment in both the double-blind and open-label study periods)

- Death in nonrandomized patients or randomized and not treated patients
- TEAE leading to death (death as an outcome on the AE CRF page, as reported by the investigator) by (at least) SOC (sorted by internationally agreed order), and PT (sorted by decreasing frequency, showing the number (n) and percentage (%) of patients) for both the double-blind and open-label study periods

#### 10.4.4.2. Laboratory Data and Vital Signs

The following definitions will be applied to laboratory parameters and vital signs:

- The baseline value is defined as the last available value before first dose of double-blind investigational study drug.
- The PCSA values are defined as abnormal values considered medically important by the sponsor according to predefined criteria/thresholds based on literature review and defined by the sponsor for clinical laboratory tests and vital signs.
- PCSA criteria will determine which patients had at least 1 PCSA during the TEAE period, taking into account all evaluations performed during the TEAE period, including unscheduled or repeated evaluations. The number of all such patients will be the numerator for the PCSA percentage.
- Double-blind treatment period: the treatment period used for quantitative analysis (laboratory results and vital signs) in the double-blind period is defined as the time from the first double-blind dose of the investigational study drug to the last double-blind dose of the investigational study drug + 21 days, or up to the first open-label dose of the investigational study drug, whichever comes first.
- Open-label treatment period: the treatment period used for quantitative analysis (laboratory results and vital signs) in the open-label study period is defined as the time from the first open-label dose of the investigational study drug to the last open-label dose of the investigational study drug + 21 days.

Summary statistics (including mean, median, Q1, Q3, standard error, minimum and maximum) of all laboratory variables and all vital sign parameters (raw data and changes from baseline) will be calculated for each visit, last and worst value assessed during the treatment period, and presented by treatment group. For selected parameters, mean changes from baseline with the corresponding standard error will be plotted over time (at same time points) in each treatment group.

The incidence of PCSAs at any time during the TEAE period will be summarized by treatment group for the double-blind study period, and by all patients and by the as-treated treatment group for the open-label study period, whatever the baseline level and/or according to the following baseline categories:

- Normal/missing
- Abnormal according to PCSA criterion or criteria

For laboratory parameters for which PCSA criterion is not defined, similar table(s) using the normal range could be provided.

**Hepatitis C Test**

The number and percentage of patients with an observed seroconversion for the hepatitis C test will be provided by treatment group for the double-blind study period, and by all patients and also by treatment group of double-blind period for the open-label study period.

**10.4.4.3. Treatment Exposure**

The double-blind duration of treatment exposure will be calculated for each of the 2 treatment arms as:

- Duration of alirocumab exposure in weeks defined as: (last double-blind study treatment administration date + 14 – first double-blind study treatment administration date)/7, regardless of unplanned intermittent discontinuations.
- The total number of double-blind treatment injections by patient.

The double-blind study treatment duration of exposure, measured in weeks, will be summarized by at least mean, median, SD, and minimum/maximum. The categorical data of number of injections will be summarized by patient counts and percentages.

The OLE duration of treatment exposure will be calculated for each of the 2 treatment arms of the double-blind period as well as patient total:

- Duration of open-label alirocumab exposure in weeks defined as: (last open-label alirocumab treatment administration date + 14 – first open-label alirocumab treatment administration date)/7, regardless of unplanned intermittent discontinuations.
- The total number of open-label alirocumab treatment injections by patient.

The open-label duration of exposure measured in weeks will be summarized by at least mean, median, SD, and minimum/maximum. The categorical data of number of injections will be summarized by patient counts and percentages.

The combined duration of treatment exposure for patients who received the alirocumab treatment in the double-blind period is calculated as:

- Combined duration of alirocumab exposure in weeks defined as: double-blind treatment exposure plus open-label treatment exposure, regardless of unplanned intermittent discontinuations.
- Combined total number of alirocumab treatment injections by patient defined as: total number of double-blind injections plus total number of open-label injections for each patient.

The combined duration of exposure measured in weeks will be summarized by at least mean, median, SD, and minimum/maximum. The categorical data of number of injections will be summarized by patient counts and percentages.

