## 7.2. Investigational and Reference Treatments

### Double-blind-Treatment:

Study drug administration during the double-blind treatment period will start on the day of randomization and will be administered immediately after completion of the LDL apheresis procedure (if applicable). For those patients not undergoing LDL apheresis, administration of the investigational study drug must be made after all samples for clinical laboratory evaluation have been obtained. The last injection of double-blind study drug will occur on day 71/week 10.

If a dose is missed, the patient will be instructed to administer the injection within 7 days from the missed dose. If the missed dose is not administered within 7 days, the patient will be instructed to skip the dose and resume the original schedule.

Patients will be randomized in a 2:1 ratio to receive:

- alirocumab 150 mg SC Q2W

OR

- matching placebo SC Q2W

Sterile alirocumab drug product will be supplied at a concentration of 150 mg/mL in a prefilled pen.

Placebo will also be supplied in a prefilled pen.

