#### **4.5. Study Treatment Exposure and Compliance Variables**

Study treatment exposure variables for injections administered during the double-blind period are listed below with associated definitions:

- Duration of double-blind study treatment exposure in weeks defined as: (last double-blind study treatment administration date +14 – first double-blind study treatment administration date)/7, regardless of unplanned intermittent discontinuations. Values will be rounded to one decimal place.
- The total number of double-blind study treatment injections by patient.
- The following categories will be used for treatment exposure intervals:  $\geq 1$  day and  $<4$  weeks,  $\geq 4$  weeks and  $<8$  weeks,  $\geq 8$  weeks and  $<10$  weeks,  $\geq 10$  weeks.

Study treatment exposure variables for injections administered during the open-label period are listed below with associated definitions:

- Duration of open-label study treatment exposure in weeks defined as: (last open-label alirocumab treatment administration date +14 – first open-label alirocumab treatment administration date)/7, regardless of unplanned intermittent discontinuations. Values will be rounded to one decimal place.
- The total number of open-label alirocumab treatment injections by patient.
- The following categories will be used for treatment exposure intervals:  $\geq 1$  day and  $<4$  weeks,  $\geq 4$  weeks and  $<8$  weeks,  $\geq 8$  weeks and  $<10$  weeks,  $\geq 10$  weeks.

Study treatment exposure variables combining double-blind and open-label periods are listed below for all patients who received alirocumab in the double-blind period:

- Combined duration of alirocumab exposure in weeks defined as: double-blind treatment exposure plus open-label treatment exposure, regardless of unplanned intermittent discontinuations.
- Combined total number of alirocumab treatment injections by patient defined as: total number of double-blind injections plus total number of open-label injections for each patient.
- The following categories will be used for treatment exposure intervals:  $\geq 1$  day and  $<4$  weeks,  $\geq 4$  weeks and  $<8$  weeks,  $\geq 8$  weeks and  $<12$  weeks,  $\geq 12$  weeks and  $<16$  weeks,  $\geq 16$  weeks and  $<20$  weeks,  $\geq 20$  weeks and  $<22$  weeks,  $\geq 22$  weeks.

Compliance will be assessed using the variables below with associated definitions.

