#### 4.7.1. Adverse Events Variables

The period of safety observation starts from the time when the patient gives informed consent and continues into the following periods:

- The PRE-TREATMENT period: defined as the time from the signed informed consent up to the first double-blind study treatment injection.
- The double-blind treatment-emergent adverse event (TEAE) period: defined as the time from the first double-blind study treatment injection up to the day of the last double-blind study treatment injection + 70 days (10 weeks), or up to the day before first dose of open label investigational study drug administration, whichever is earlier.

The double-blind TEAE period will include:

- The TREATMENT period is defined as the time from the first double-blind study treatment injection up to the day of last double-blind study treatment injection + 21 days, as serum concentration of alirocumab >10 µg/mL is expected for approximately 21 days following administration of 150 mg. Further, in previous studies, alirocumab concentrations declining below this concentration also showed a decrease in effect on LDL-C. For patients entering into the open-label period, the treatment period will be truncated at the day before the first dose of open label investigational study drug administration.
- The RESIDUAL TREATMENT period is defined as the time from the day of last double-blind study treatment injection + 22 days up to the day of last double-blind study treatment injection + 70 days (10 weeks), or up to the day before first dose of open label investigational study drug administration, whichever is earlier.
- The open-label treatment-emergent adverse event (TEAE) period is defined as the time from first open label study treatment injection up to the day of the last open-label study treatment injection + 70 days.

The open-label TEAE period will include:

- The TREATMENT period is defined as the time from the first open-label study treatment injection up to the day of last open-label study treatment injection + 21 days.
- The RESIDUAL TREATMENT period is defined as the time from the day of last open-label study treatment injection + 22 days up to the day of last open-label study treatment injection + 70 days (10 weeks).
- The POST-TREATMENT period: defined as starting the day after the end of the respective TEAE periods up to the patient's end of study.

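### Double-blind exposure is not stopped at the first open-label injection, so when that injection comes less than 14 days after the last double-blind one, the overlapping days are counted twice in combined alirocumab exposure

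*Protocol*

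**What the plan says.** Protocol 10.4.4.3 computes double-blind duration, for each of the two arms, as "last double-blind study treatment administration date + 14 – first double-blind study treatment administration date)/7". Open-label duration is "last open-label alirocumab treatment administration date + 14 – first open-label alirocumab treatment administration date)/7". For patients randomized to alirocumab the two are added: "Combined duration of alirocumab exposure in weeks defined as: double-blind treatment exposure plus open-label treatment exposure, regardless of unplanned intermittent discontinuations".

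SAP 4.5 keeps these rules. Its entry "Duration of double-blind study treatment exposure in weeks defined as" is followed by the same expression, "last double-blind study treatment administration date +14 – first double-blind study treatment administration date)/7", and its combined measure is again a plain sum: "Combined duration of alirocumab exposure in weeks defined as: double-blind treatment exposure plus open-label treatment exposure". It rounds the double-blind and open-label durations to one decimal place of a week.

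Most other double-blind periods in these documents end when open-label dosing starts. For the treatment period, SAP 4.7.1 says "the treatment period will be truncated at the day before the first dose of open label investigational study drug administration". The efficacy treatment period (Protocol 4.2.2.2, SAP 4.6.3), the TEAE period (Protocol 10.4.4.1, SAP 4.7.1), the laboratory and vital-signs period (Protocol 10.4.4.2) and double-blind concomitant medications (SAP 4.3) also stop there. The exposure duration does not.

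**The concern.** The 14-day tail credits the last double-blind injection with one full dosing interval. Open-label exposure starts its own count at the first open-label injection. If that injection comes before the tail has run out, the same calendar days sit in both terms of the sum.

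The documents allow this. Protocol 8.2.1 gives the week 10 dose a window of ±3 days off apheresis and +1 day on apheresis, and Table 1 allows the Day 85 visit to be early. The late-dose rule adds to it: "If a dose is missed, the patient will be instructed to administer the injection within 7 days from the missed dose". The original schedule then resumes, so the next interval is short.

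Two reported quantities are exposed. Combined alirocumab exposure can be longer than the calendar time from first injection to the end of the open-label tail. In the placebo arm, double-blind exposure can include days on which the patient was already receiving open-label alirocumab.

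**Working it through.** **Inputs.** The first double-blind injection is on Day 1, the last on Day 71; the first open-label injection is on Day 85, the last on Day 155 (Protocol synopsis). The week 10 dose window is ±3 days off apheresis and +1 day on apheresis (Protocol 8.2.1); Table 1 prints ±5/±1 for the Day 71 visit. The Day 85 visit window is ±3/±1 (Table 1). A dose up to 7 days late is still given (Protocol 7.2 and 8.2.1).

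**Formulas.**
- DB = (last DB + 14 − first DB)/7
- OL = (last OL + 14 − first OL)/7
- Combined = DB + OL
- Days counted twice = max(0, last DB + 14 − first OL) = max(0, 14 − gap)
- Capped DB = (min[last DB + 14, first OL] − first DB)/7

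**Planned schedule.** DB = (71 + 14 − 1)/7 = 12.0. OL = (155 + 14 − 85)/7 = 12.0. The sum is 24.0 weeks, which reproduces the planned 24 weeks. Days counted twice: 71 + 14 − 85 = 0.

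**Off schedule**, with the last open-label dose held at Day 155, so that calendar time is (155 + 14 − 1)/7 = 24.00 weeks:

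| Case | Last DB | First OL | Counted twice | DB, weeks | Capped DB | Combined | Capped combined | Excess in combined |
|---|---|---|---|---|---|---|---|---|
| Off apheresis, ±3 limits | 74 | 82 | 6 days | 12.43 | 11.57 | 24.86 | 24.00 | 3.6% |
| Off apheresis, Table 1 ±5 | 76 | 82 | 8 days | 12.71 | 11.57 | 25.14 | 24.00 | 4.8% |
| On apheresis | 72 | 85 | 1 day | 12.14 | 12.00 | 24.14 | 24.00 | 0.6% |
| On apheresis | 72 | 84 | 2 days | 12.14 | 11.86 | 24.29 | 24.00 | 1.2% |
| 7 days late, early visit | 78 | 82 | 10 days | 13.00 | 11.57 | 25.43 | 24.00 | 6.0% |
| Gap over 14 days | 68 | 88 | 0 days | 11.57 | 11.57 | 23.14 | 23.14 | 0% |

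For the first row: 74 + 14 − 82 = 6 days; DB = 87/7 = 12.43; OL = (155 + 14 − 82)/7 = 12.43; the sum is 24.86. A placebo patient with the same dates would have 12.43 instead of 11.57 weeks of double-blind exposure (+7.4%).

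**Average, off apheresis.** The documents give no distribution of dosing dates. Assume both dates are independent and uniform within ±3 days. In continuous time the mean overlap is E|U1 − U2|/2 = 2/2 = 1.0 day, and 1.0/168 = 0.6% of combined exposure. In whole days, 21 of the 49 date pairs overlap (43%), and the mean is 56/49 = 1.1 days. This average does not apply to patients on apheresis, whose windows are narrower.

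**The case against.** The strongest reply is that last dose plus one interval is a nominal convention. It already ignores intermittent interruptions, and SAP 4.7.1 expects serum alirocumab above 10 µg/mL for about 21 days after a 150 mg dose, so +14 could be called too short when the gap is 15 to 21 days. The capped periods assign events, samples or medications to a period, whereas an exposure duration assigns nothing. No planned analysis divides by it: adverse-event percentages use the safety population, time-to-event censoring uses the capped TEAE period, and the injection-site reaction rate divides by injections. The SAP's duration categories do not move for completers either. In the Day 82 cases, capped double-blind exposure of 11.57 weeks and combined exposure of 24.00 weeks stay in the top categories (10 weeks or more, and 22 weeks or more).

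Most of this stands, and it limits the point to descriptive summaries. It does not answer the double count: summed alirocumab exposure longer than calendar time is wrong under any convention. Nor do late gaps cancel it. Under the +14 rule, days beyond the tail are left uncounted by design, so a long gap in one patient does not offset an overlap in another. One day is 1/7 = 0.14 week, which shows at one decimal.

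A reader might also take any double-blind exposure above 12 weeks as a sign of the error. It is not. With the last double-blind dose on Day 74 and open-label start on Day 88, the formula gives (74 + 14 − 1)/7 = 12.43 weeks with no overlap, and the capped formula gives the same.

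**Conclusion.** The point holds conditionally. Days are counted twice only when the gap between the last double-blind and first open-label injections is under 14 days, and the number is 14 minus the gap. It would be wrong to infer that every patient's exposure is overstated: on the planned schedule, and with any gap of 14 days or more, the formulas work as intended.

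Within the ±3-day windows off apheresis the overlap is at most 6 days, or 8 days if Table 1's ±5 is used. On apheresis it is 1 to 2 days. The 10-day case needs a dose a full 7 days late and an open-label visit 3 days early, so it is a corner case. The mean of about 1 day off apheresis rests entirely on the uniform-timing assumption.

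A reader might also infer harm to efficacy or safety conclusions. The documents do not support that: injection counts, TEAE periods and efficacy analyses do not use this duration. Placebo patients are not part of combined alirocumab exposure; for them only the double-blind figure is affected. This is a minor correction that is worth making.

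**What to change.** In Protocol 10.4.4.3 and SAP 4.5, define double-blind exposure in weeks as (earlier of [last double-blind dose date + 14] and [first open-label dose date] − first double-blind dose date)/7, in both arms. Patients who never start open-label treatment keep last dose + 14. Leave combined exposure as the sum.

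The cap should be the first open-label date itself, not the day before. The formula is a difference of dates, so stopping at Day 84 would give (84 − 1)/7 = 11.86 weeks on the planned schedule instead of 12.0.

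The cost is one line of wording in each document and one line of code. No new data are needed, planned-schedule results do not change, and the Day 74/Day 82 case returns to 24.00 weeks. Reported exposure becomes slightly shorter in patients with a short gap. Separately, the week 10 windows in Table 1, its footnote 9 and Protocol 8.2.1 differ and need to be reconciled. The cap works whichever window applies.

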**10.4.4.4. Treatment Compliance**

Compliance during the double-blind period will be assessed using the following parameter: The injection frequency will be defined for each patient as the average number of days between 2

injections, that is: (last dose date – first dose date)/(number of injections -1) for patients receiving at least 2 injections.

The parameter will be summarized descriptively (N, mean, SD, median, min and max).

#### **10.4.5. Analysis of Drug Concentration Data**

Descriptive statistics of concentrations of alirocumab will be provided by treatment group. Plots of the individual concentrations of alirocumab will be presented versus actual time (linear and log scales). Plots of the mean or median concentrations of alirocumab will be presented by time point (linear and log scales).

#### **10.4.6. Analysis of Pharmacodynamics Data**

Descriptive statistics of concentrations of total PCSK9 and free PCSK9 will be provided by treatment group. Plots of the individual concentrations of total and free PCSK9 will be presented versus actual time (linear and log scales). Plots of the mean or median concentrations of total and free PCSK9 will be presented by time point (linear and log scales).

#### **10.4.7. Analysis of Anti-Drug Antibody Data**

The ADA status and ADA titers will be summarized by treatment group and visit using descriptive statistics. If appropriate, correlations between ADA titers, safety and/or efficacy endpoints will be provided.

### **10.5. Timing of Statistical Analysis**

The analyses will be conducted in 2 steps. The first analysis will be conducted as soon as all patients have been randomized and all data through week 12 (double-blind period) have been collected and validated; this will consist of the final analysis of the double-blind primary and secondary efficacy endpoints. The safety analysis will be performed on all safety data collected and validated at the time of the first analysis.

Since the double-blind primary efficacy measure data collection will have been concluded at the time of this first analysis, the significance level for the study remains at 0.05. This first analysis may be used for the submission to health authorities or other interested parties.

The second analysis will be performed with the data from the open-label treatment period and will consist of the final analysis for the safety and exploratory efficacy measures.

The results of the first analysis will not be used to change the conduct of the ongoing study in any aspect. Individuals involved in the first step analysis of the study will not be involved in the conduct of the study afterwards; individual patient identification will not be released to anyone who is directly involved in the conduct of the study. The first step analysis process, the measures used to protect the blind and the integrity of the study, the communication plan, and the confidentiality agreement will be described in a separate document.

### **10.6. Additional Statistical Data Handling Conventions**

Additional data handling conventions will be described in the statistical analysis plan.

## **10.7. Statistical Considerations Surrounding the Premature Termination of a Study**

If the study is terminated prematurely, only those parameters required for the development program and/or reporting to regulatory authorities will be summarized. Investigator and sponsor responsibilities surrounding the premature termination of a study are presented in Section 16.1.

# **11. DATA MANAGEMENT AND ELECTRONIC SYSTEMS**

## **11.1. Data Management**

A data management plan specifying all relevant aspects of data processing for the study (including data validation, cleaning, correcting, releasing) will be maintained and stored at Regeneron.

A medical coding plan will specify the processes and the dictionary used for coding. All data coding (eg, AEs, baseline findings, medication, medical history/surgical history/ophthalmic history) will be done using internationally recognized and accepted dictionaries.

The CRF data for this study will be collected with an electronic data capture (EDC).

